Negative Urgency will be assessed using the Urgency, Premeditation, Perseverance, Sensation Seeking, Positive Urgency, Impulsive Behavior Scale.⁷⁶ Participants will complete visual analog scale (VAS) questions related to spontaneous pain and pain with movement, with each line being anchored with 'none' on the left and 'worst imaginable' on the right.⁷⁷ Additionally, participants will complete several pain experience visual analog scales (PEVAS); the PEVAS includes seven 10-cm lines that measure a different component of the pain experience (i.e. depression, anxiety,

frustration, fear, anger, pain intensity, pain unpleasantness) with a written description of 'none' on the left and 'worst imaginable' on the right. The PEVAS will measure pain-related negative affect, and participants will provide their rating by placing a mark along each line. Expectancies of muscle soreness from the exercises involved in this study will be assessed with a VAS-style question anchored by 'no muscle soreness' and 'most intense muscle soreness imaginable.' In addition, expectancies of analgesia from alcohol and marijuana, as well as urge to consume alcohol and marijuana, will also be measured using VAS-style questions, with lines being anchored by 'no pain relief at all' and 'complete pain relief' for expectancies of analgesia and lines being anchored by 'no urge' and 'very strong urge' for urge-related questions. History of self-medication behaviors will be assessed using separate VAS-style questions measuring likelihood of using alcohol or marijuana when experiencing pain in the past. Each line will be anchored by 'none of the time' and 'all of the time'. Other measures will assess alcohol use patterns (Alcohol Use Disorders Identification Test,⁷⁸ Alcohol Use Questionnaire⁷⁹), marijuana use patterns (Cannabis Use Disorder Identification Test, Revised,⁸⁰ Daily Sessions, Frequency, Age of Onset, and Quantity of Cannabis Use Inventory⁸¹), and use of other substances (NIDA Modified Alcohol, Smoking and Substance Involvement Screening Test,⁸² Fagerstrom Test for Nicotine Dependence⁸³). Finally, a single-item question will measure frequency of simultaneous alcohol and marijuana use behaviors over the past 12 months.⁸⁴

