Participants who continue to qualify following completion of screening procedures and agree to proceed will be assigned to either the *DOMS* or *Sham DOMS* group. Assignments will be made according to a participant's unique subject identifier using a spreadsheet listing group assignment in pseudo-random order using the Excel random number function.

Participants will then complete the Alcohol Purchase Task (APT), Marijuana Purchase Tasks, (MPT), and DOMS or sham DOMS induction procedures. They will also be will be scheduled for a second lab session 48 hours later so that potential changes in DOMS-associated alcohol and marijuana demand can be investigated. Participants who complete the screening but either do not qualify or decide not to proceed will be paid \$15 via gift card. Those who do qualify and proceed with the study will be paid \$50 at the end of the first lab visit and \$15 at the end of the second lab visit. For the daily surveys, compensation was provided as a function of the number of surveys completed, with a maximum of \$30 for participants who completed 5/7 or more of their assessments (see "Daily Measures" section for additional information). We will also ask whether their DOMS (if any) has resolved with the daily measures. Additionally, participants who refer an individual to the study that attends the screening session will also receive \$20 per person referred. The referee(s) will be responsible for contacting the study team via phone or email in order to schedule the session. The referrer will receive the \$20 bonus once the person they refer attends their screening session, whether or not they eventually decide to participate. All participants who provide informed consent will be eligible to refer participants to the study regardless of whether they qualify to proceed after screening procedures.

Alcohol Purchase Task (APT) and Marijuana Purchase Tasks (MPT)

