Figure 1. BiodeX setup for isometric strength and DOMS.

DOMS-inducing exercise protocol. To perform the dynamic fatiguing exercise bout, the participant will be seated in the BiodeX machine in order to isolate elbow flexion. The participant will perform the isometric strength test (described above). Following 60 seconds of rest after the isometric test, participants will complete an exercise protocol consisting of eccentric (elbow straightening/biceps lengthening) exercises designed to induce DOMS at the biceps. **Participants in the DOMS group will perform 3 sets of 15 repetitions at a speed of 60°/s. Participants in the Sham DOMS group will complete one set of 15 concentric (elbow flexion/biceps shortening) repetitions at**

a resistance set to 30% of their maximum voluntary contraction, which is unlikely to induce significant DOMS.

DOMS-related Pain Measures

Upon arriving in the laboratory for their second study session, participants will complete several measures regarding pain associated with the exercise protocol.

1. Pain Experience: Pain experience visual analog scales (PEVAS) include seven 10-cm lines that measure a different component of the pain experience (i.e. depression, anxiety, frustration, fear, anger, pain intensity, pain unpleasantness) with a written description of 'none' on the left and 'worst imaginable' on the right. The PEVAS will measure pain-related negative affect, and participants will provide their rating by placing a mark along each line.

2. Pain with Movement: Participants will also rate pain during elbow extension and elbow flexion using the same scale. This will give ratings of both spontaneous pain and pain with movement.

Daily Measures

Participants will receive instructions related to the daily electronic diary following DOMS induction. These measures will primarily be used evaluate the pain associated with DOMS and assess alcohol and marijuana use following the exercise protocol.

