Participants will receive a text message with a link to the REDCap survey every night for one week, and text messages will begin the day of the first lab visit. The daily assessment will be personalized, such that participants will inform study staff of preferences for when they receive the survey each night before bed. Prior to leaving lab session 1, participants will be sent a practice text message to ensure that they receive it. Individuals who fail to complete their daily diary will be prompted via a reminder text or telephone call. Participants will provide daily reports of 1) Pain Experience VASs, 2) VAS questions related to spontaneous pain and pain with movement, 3) the number of standard alcoholic drinks they have consumed, 4) route of administration (ROA) of marijuana use and number of hits taken according to route of administration (in checklist form to allow for endorsement of multiple ROAs of marijuana use), and 5) number of hours "high." If a participant endorses marijuana use by a non-inhalational ROA (e.g. edibles, tinctures, topicals), they will be prompted with a free-response question to describe the quantity of their marijuana use in as much detail as possible. A single yes/no item will inquire about whether alcohol and marijuana were used simultaneously, such that their effects overlapped, and participants will also report the intensity of their "high" from marijuana via a VAS-style question with 'not at all high' on the left and 'extremely high' on the right. Additionally, participants will report whether or not other substances (e.g. tobacco, cocaine, hallucinogens) or over-the-counter and prescription pain medications were used. They will also indicate the extent to which pain interfered with several domains (e.g. general activity, walking ability, enjoyment of life, sleep) over the past 24 hours.

Study Design

The overall design of the study is detailed in Figure 2.

[figure not shown]

Figure 2. Study design flowchart.

Data Analysis Strategy

Data will be collected in a Research Electronic Data Capture (REDCap) database and analyzed using IBM SPSS 25.

Aim 1: Determine impact of DOMS pain on demand for alcohol and marijuana and examine race and sex as moderators of this relationship.

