Hypotheses for DOMS-related changes in alcohol and marijuana demand indices (persistence and amplitude) will be assessed using separate 2 (group: DOMS vs. sham DOMS) x 2 (sex: men vs. women) x 2 (race: White vs. Black) x 2 (time: visit 1 vs. visit 2) repeated measures analysis of variance (ANOVA). Identical ANOVAs will examine changes in marijuana demand indices.

Aim 2: Identify psychosocial factors associated with change in demand for alcohol and marijuana after DOMS induction.

To test the hypothesis that negative affect mediates the relationship between DOMS pain and increased alcohol and marijuana demand, Pearson correlations will be conducted to examine continuous relationships between measures of pain, pain-related negative affect (e.g. pain experience VASs), and change in alcohol and marijuana demand. A series of linear regressions will then be conducted to examine 1) the effect of group (DOMS vs. sham DOMS) on change in alcohol and marijuana demand, and 2) the effect of group and pain-related negative affect on change in alcohol and marijuana demand. We will test the significance of indirect effects of pain-related negative affect using PROCESS, a custom macro in SPSS.

To examine the hypothesis that greater expectancy of analgesia from marijuana or alcohol use, higher negative urgency, and history of self-medication behaviors will predict greater change in demand, a simultaneous multiple linear regression analysis will be conducted with these variables as predictors in the model.

Power Analysis

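### Aim 2 names no time point for pain-related negative affect and makes no use of the pre-induction ratings, so the affect-to-demand slope and the indirect effect can mix standing affect with the DOMS response

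*Combined protocol and SAP*

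**What the plan says.** **Before induction.** Screening Measures (section 6) states: "Participants will complete visual analog scale (VAS) questions related to spontaneous pain and pain with movement". It adds that "participants will complete several pain experience visual analog scales (PEVAS". No joint is named for the movement item, and the PEVAS lines are not tied to the exercised arm. Group assignment follows screening, and only after that: "Participants will then complete the Alcohol Purchase Task (APT), Marijuana Purchase Tasks, (MPT), and DOMS or sham DOMS induction procedures". The visit-1 ratings are therefore true baselines.

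**At 48 hours.** DOMS-related Pain Measures states: "Upon arriving in the laboratory for their second study session, participants will complete several measures regarding pain associated with the exercise protocol". The PEVAS is repeated, and for movement pain "Participants will also rate pain during elbow extension and elbow flexion using the same scale".

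**In the diary.** Daily Measures adds a third source, nightly for a week: "Participants will provide daily reports of 1) Pain Experience VASs".

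**In the analysis.** The Data Analysis Strategy for Aim 2 uses Pearson correlations to "examine continuous relationships between measures of pain, pain-related negative affect (e.g. pain experience VASs), and change in alcohol and marijuana demand". It then regresses change in demand on group, and next models "the effect of group and pain-related negative affect on change in alcohol and marijuana demand". PROCESS tests the indirect effect. Demand is expressed as change. For pain and affect the text gives no time point, does not choose between level and change, and lists no covariate.

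**The concern.** Aim 2 asks whether the negative affect produced by DOMS carries the effect of DOMS pain to demand. A rating made at 48 hours contains that response and also whatever depression, anxiety, frustration, fear or anger the person already reported at visit 1. Group is randomised but affect is not. If people with higher usual affect also tend to shift their demand between visits, the slope of demand change on visit-2 affect absorbs that association even when the response to exercise has no effect. If usual affect is unrelated to demand change, it dilutes a true slope instead. Either way the indirect effect, which is the product of the group-to-affect path and this slope, no longer describes the DOMS response alone. The variable needed to separate the two is already collected.

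**Working it through.** **The plan's own figure.** The only sample-size figure is N = 56 (Power Analysis), and it concerns the repeated-measures ANOVA. The pilot amplitude effect checks: 3.13/(3.13 + 36) = 0.080. This gives f = √(0.08/0.92) = 0.295. With two time points, correlation 0.5, α = 0.05, power 0.80 and eight group × sex × race cells, the minimum N is 49, which becomes 56 as a multiple of eight (power 0.871 at 56). The eight cells and this choice of f are inferred; they are the combination that matches. No power is stated for the Aim 2 mediation.

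**Inputs for the check.** From the plan: N = 56 and α = 0.05. Assumed, because the documents are silent: 28 per arm, no dropout, normal data, a group effect on affect of 0.8 SD, and a visit-1 to visit-2 correlation r of 0.3, 0.5 or 0.7.

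**Null scenario.** The affect response has no effect on demand, but baseline affect predicts demand change by 0.3 SD per SD. Write M1 for visit-1 affect and M2 for visit-2 affect, each with within-group variance 1.

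- Level of M2, no baseline term: expected slope = 0.3 × r = 0.09, 0.15, 0.21. Standard error ≈ √[(1 − slope²)/53] = 0.137, 0.136, 0.134, so slope/SE = 0.66, 1.10, 1.56. From the noncentral t with 53 degrees of freedom, the false-positive rate is 9.9%, 19.2%, 33.6%. Simulation gives 10%, 20%, 34%. If the residual variance rather than the total is set to 1, the rates are 9%, 18%, 32%.
- M1 added as covariate: expected slope 0, false-positive rate about 5%.
- Change score M2 − M1: expected slope = 0.3(r − 1)/[2(1 − r)] = −0.15 at every r. The false-positive rate is about 25%, 19%, 14%.

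If baseline affect predicts a fall in demand, the signs reverse and the rates stay the same. All these rates are for the slope; the PROCESS test of the indirect effect was not simulated.

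**Dilution scenario.** Baseline affect is unrelated to demand change and the response has a true slope of 0.40. The unadjusted slope is 0.40 × (1 − r²) = 0.36, 0.30, 0.20; with M1 added it is 0.40. The false-positive rate under no true effect stays near 5% in this case.

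A different model gives different numbers. Let M1 = T + e and M2 = T + S plus a group effect, with var(T) = r, var(S) = var(e) = 1 − r, and only S and the group-produced part driving demand. The unadjusted slope recovers 1 − r = 70%, 50%, 30% of the truth. With M1 as covariate it recovers (1 − r)/(1 − r²) = 1/(1 + r) = 77%, 67%, 59%. When M1 is a noisy measure of standing affect, the covariate helps but does not fully repair the slope.

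**Group-to-affect path.** It is unbiased either way (simulated mean about 0.80 for a true 0.80). Adjustment only sharpens it. The minimum detectable difference at 80% power is (1.960 + 0.842) × √(2/28) = 0.75 SD, and multiplying by √(1 − r²) gives 0.71, 0.65, 0.53 SD.

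**The case against.** A reader might infer that the plan commits to uncorrected visit-2 levels. It does not. The analysis text is silent on time point and on level versus change; visit 2 is implied by the heading and content of DOMS-related Pain Measures, and diary ratings also exist. What can be said is that the choice is open and no baseline term is listed. The candidate versions are not equivalent, as the level and change-score results show.

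A reader might also infer that the group comparisons are biased. They are not: assignment is pseudo-random with a sham arm, and group is in the mediation regression. Aim 1 is untouched.

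Unrelated pain is the weaker part of the case. Visit-2 movement pain is rated at the elbow, the visit-2 scales are introduced as concerning the exercise, and the PEVAS asks about components of pain experience rather than general mood. Table 1 excludes recent wrist/hand, elbow or shoulder pain, chronic conditions affecting pain perception, and self-reported major psychiatric disorder. Recent use of pain medication can lead to rescheduling or discontinuation. Milder distress and everyday pain elsewhere remain possible, but the exposure is narrower than the scale list alone suggests. In such a sample many visit-1 ratings may sit near zero, and the gain from adjustment would then be small.

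Finally, the size rests entirely on assumed correlations and on the model chosen. That stands. It limits what can be claimed about magnitude, but not the case for a nearly free adjustment.

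**Conclusion.** The point holds as a gap in the Aim 2 analysis: the mediator's time point is unstated and a relevant baseline, already measured, is unused. The exposed quantities are the pain and affect correlations, the affect-to-demand slope and, through it, the indirect effect. Under the stated assumptions the slope's false-positive rate is about 10%, 20% or 33% for r of 0.3, 0.5 or 0.7, against about 5% after adjustment. Where baseline affect does not predict demand change, the cost is dilution rather than false positives. The documents support neither a claim that the bias is present nor a particular size for it. Correction is worthwhile because mediation is a stated hypothesis of one of the two specific aims.

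**What to change.** In the Aim 2 analysis text:

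1. State that the visit-2 PEVAS affect score is the mediator.
2. Add the visit-1 PEVAS affect score as a covariate in both the mediator and the outcome equations in PROCESS, and in the matching regression.
3. Replace the simple Pearson correlations for PEVAS affect and spontaneous pain with partial correlations adjusted for the visit-1 value of the same measure.
4. For movement pain, adjust for the visit-1 item only if it is the same elbow-movement rating. The documents do not show that it is.
5. Do not substitute a simple change score for the covariate.

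The cost is a few sentences and one degree of freedom per model. No new data are needed.

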Aim 1. Determine impact of DOMS pain on demand for alcohol and marijuana and examine race and sex as moderators of this relationship.

We predict that those who undergo the DOMS induction paradigm will show greater increases in alcohol and marijuana demand than participants in the sham DOMS control group. We also predict an interactive effect of race and sex on DOMS-related changes in alcohol and marijuana demand, such that increases may be greater in White men than Black women and men, as well as White women.

Aim 2. Identify psychosocial factors associated with change in demand for alcohol and marijuana after DOMS induction.

Consistent with current evidence,^{42, 67} we predict that pain-related negative affect will mediate the association between DOMS-related pain and increased demand for alcohol and marijuana. We also predict that greater expectancy of analgesia from marijuana or alcohol use, higher negative urgency, and history of self-medication behaviors will predict greater change in alcohol and marijuana demand.

6. Research Plan:

Participants

We will recruit participants aged 21 years and older who are regular co-users of alcohol and marijuana (i.e., concurrent or simultaneous use at least 2-3 times per week over the past 6 months). Extent of co-use will be determined using the Alcohol Use Disorders Identification Test (AUDIT) and Cannabis Use Disorder Identification Test, Revised (CUDIT-R). A research team member will inform participants of inclusion and exclusion criteria via email or the phone. If an individual believes they meet all study criteria, they will be scheduled for the first study session (see Phone and Email Scripts for details). We will review all inclusion and exclusion criteria one additional time with participants before initiating the Informed Consent process.

Inclusion/Exclusion Criteria

Detailed inclusion/exclusion criteria are provided in Table 1.

Table 1. Inclusion and exclusion criteria
Inclusion Criteria 
• Aged 21-65 years;• English-speaking• Self-identify as White/Caucasian or Black/African American• Own a smartphone with cellular/data plan• Regularly co-use alcohol and smoked marijuana as indicated by scores of ≥ 3 on item 1 of the CUDIT-R and AUDIT.• Willing and able to give informed consent

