Exclusion Criteria 
• Participation in exercises that involve the biceps in the past 6 months*• Self-reported wrist/hand, elbow, or shoulder pain the past 3 months• Chronic medical condition that may affect pain perception (e.g. diabetes, fibromyalgia, headaches)• Self-reported kidney dysfunction, muscle damage, or major psychiatric disorder• Medical marijuana prescription, recommendation, or card• Consumption of marijuana using only non-inhalational methods (e.g. edibles, tinctures, or cannabidiol oil)• Women who are pregnant, trying to become pregnant, or breastfeeding

*Examples include bicep curls, pull-ups, olympic weightlifting, etc.

In addition, participants who indicate they have consumed of any drugs (e.g., alcohol, theophylline, tranquilizers, over-the-counter and prescription pain medications, including NSAIDs and opioids) that may affect pain perception or hydration status 24 hours before participation in a testing session or used caffeine 4 or less hours before testing session will be discontinued or rescheduled at the PI's discretion. Additionally, participants who report that they have used any tobacco products less than 1 hour before participation in a testing session will be discontinued or rescheduled at the PI's discretion.

Screening Procedure

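### The Aim 2 mediation model holds only group and negative affect, so the affect-to-demand path may be confounded by baseline traits that are already measured but left out

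*Combined protocol and SAP*

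**What the plan says.** The plan for mediation is in Section 6, Data Analysis Strategy, Aim 2. After Pearson correlations, one regression relates change in demand to group, and a second estimates "the effect of group and pain-related negative affect on change in alcohol and marijuana demand". Then: "We will test the significance of indirect effects of pain-related negative affect using PROCESS, a custom macro in SPSS". No covariate, model number, bootstrap setting or sensitivity analysis is given.

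Section 5, Aim 2 also predicts that greater analgesia expectancy, "higher negative urgency, and history of self-medication behaviors will predict greater change in alcohol and marijuana demand". These traits are analysed separately: "a simultaneous multiple linear regression analysis will be conducted with these variables as predictors in the model". As described, that regression contains neither group nor negative affect.

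The traits are measured before assignment (Section 6, Screening Measures): "Negative Urgency will be assessed using the Urgency, Premeditation, Perseverance, Sensation Seeking, Positive Urgency, Impulsive Behavior Scale", and "History of self-medication behaviors will be assessed using separate VAS-style questions". Analgesia expectancy for each substance, the Pain Catastrophizing Scale and the pain experience scales (PEVAS) are collected at the same stage. Group is then allocated "using a spreadsheet listing group assignment in pseudo-random order using the Excel random number function". The PEVAS rating taken on arrival at the second session, under DOMS-related Pain Measures, is the natural mediator; demand is measured again at that session.

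**The concern.** An indirect effect is the product of two paths. Assignment protects the path from group to affect, and the total effect of group on demand. It does not protect the path from affect to demand, because participants are not assigned their level of distress. Within an arm, those who report more distress may differ in stable ways from those who report less.

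If such a trait also drives change in demand, affect and demand change will be correlated even when affect does nothing. The two-variable model would credit that correlation to affect and could report mediation. If the trait pushes affect and demand in opposite directions, the model could miss a real path.

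Mediation is the first hypothesis of Aim 2, and the Background frames the work as a study of causal pathways. The trait-only regression does not help, since its results do not enter the mediation estimate.

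**Working it through.** **The plan's own figure.** The only one is the total of 56 (Power Analysis: alpha .05, power .80, correlation .5), and it is not given for mediation. It can be reproduced for Aim 1. Take f² = .08/.92, so f = .295, with 8 between-subject cells and 2 visits. The G*Power within-between interaction (λ = f²·N·2/(1 − .5), df 7 and N − 8) needs N = 49; the next multiple of 8 is 56. The cell count and choice of f are inferred. N = 56 is used below as an input.

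**Inputs.** From the plan: N = 56 and a model with group and affect only. Assumed, because the documents give no values: 28 per arm, an arm effect of 1 SD on affect, and within-arm correlations r(T,M) of trait T with affect M and r(T,Y) of trait T with demand change Y.

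**Size of the bias.** Within arm, with M and Y standardised and a true path b = 0, the fitted path is

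b* = Cov(M,Y)/Var(M) = r(T,M) × r(T,Y).

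Equal correlations of .3, .4 and .5 give .09, .16 and .25. If either correlation is zero, b* = 0.

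**False mediation.** Both paths p < .05, true b = 0, 20,000 simulated trials per setting:

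| r (both links) | Trait omitted | Trait included |
|---|---|---|
| 0 | 4.6% | 4.6% |
| .1 | 4.9% | 4.9% |
| .2 | 5.8% | 5.0% |
| .3 | 9.4% | 4.7% |
| .4 | 20.7% | 5.0% |
| .5 | 43.8% | 4.7% |

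Unequal links: r(T,Y) = .5 with r(T,M) = 0 gives 4.9%, and with r(T,M) = .1 gives 6.2%.

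**Bootstrap check.** A percentile bootstrap (1,500 trials, 500 resamples) at r = .3, .4 and .5 gives 8.8%, 17.7% and 37.5% for an arm effect of 0.8 SD, and 12.3%, 24.5% and 48.3% for 1.2 SD. With the trait included, all six rates lie between 4.4% and 6.8%.

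**Trait acting only under pain.** Let the trait affect both M and Y in the DOMS arm only, with sham-arm affect compressed (SD 0.3). At r = .3, .4 and .5:
- trait omitted: 7%, 12% and 23%;
- trait as a main effect: 5%, 6% and 9%;
- trait-by-group term added: 4% to 5%.

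**Masking.** With a true b of .4 and no confounding, power is about .77. Opposite-sign correlations of .3 and .4 shrink the fitted path to .4 − .09 = .31 and .4 − .16 = .24, and power falls to about .57 and .40. Including the trait restores about .78.

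**Cost.** Residual degrees of freedom in the outcome equation are 56 − 3 = 53 now, 49 with four covariates and 48 with five. If all the covariates are unrelated to affect and demand, power at b = .4 falls from about .77 to about .73 with four and .72 with five.

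**The case against.** The strongest reply is that the documents supply only half of a confounder. They predict that three traits drive change in demand, but nowhere link those traits to pain-related affect. A reader might infer that the planned test must be biased if the plan's own trait hypotheses are true. That does not follow: a trait strongly tied to demand change but unrelated to affect leaves the error rate at its nominal level. The second link is a judgement. It is most plausible for negative urgency and less obvious for expectancy and self-medication history. For catastrophizing the gap is the reverse: a link to distress is plausible, but the plan does not predict that it drives demand. This objection stands and makes the concern conditional.

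The larger rates also need strong assumptions. The outcome is a change score, which removes stable trait effects on the level of demand, so r = .5 on both links would be high. At r = .1 to .2 the inflation is negligible. This stands too, and is why the range starts low.

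A reader might further infer that adjusting for visit-1 PEVAS would be useless, because enrolment excludes "Self-reported wrist/hand, elbow, or shoulder pain the past 3 months" and affect would then sit at its floor. The documents give no visit-1 values, and five of the seven PEVAS lines rate emotions. There is no ground for dismissing that baseline.

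None of this gives a reason to leave out measured, pre-assignment traits from a model whose second path is observational.

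**Conclusion.** The concern holds as a conditional one. The planned mediation test may be confounded if a baseline trait that drives change in demand also raises pain-related distress. The first link is the plan's own prediction; the second is an assumption. False mediation then ranges from about 5% or 6% at r = .1 to .2 up to about 44% at r = .5, and opposite-sign confounding can cut power from about .77 to between .57 and .40. These figures rest on 28 per arm, a 1 SD arm effect on affect, one omitted trait and equal-sized correlations. The documents fix none of these.

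Aim 1, the total group effect and the sample size are unaffected. The change should be made because it is cheap and is best settled before the data are seen.

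**What to change.** In Section 6, Data Analysis Strategy, Aim 2:

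- Enter pre-assignment covariates in both PROCESS equations (affect and demand change) and in the matching regressions: negative urgency, analgesia expectancy and self-medication history for the substance analysed, and the Pain Catastrophizing Scale. Consider visit-1 PEVAS negative affect as a fifth.
- Report the group-and-affect model alongside the adjusted one.
- Add a trait-by-group term as a sensitivity analysis, because a main effect does not fully handle a trait that acts only under pain.
- State that the indirect effect still assumes no unmeasured confounding of affect and demand change.

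All these measures are already collected at screening and PROCESS accepts covariates, so only the analysis text changes. The price is four or five residual degrees of freedom and, if the covariates turn out to be unrelated, about 4 to 5 points of power.
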